## 10.3 Endpoints

### 10.3.1 Primary Endpoint

- Proportion of participants who achieve  $\geq 1$  stage improvement in liver fibrosis (NASH CRN Fibrosis Score), as determined by liver biopsy after 12 weeks of treatment

### 10.3.2 Secondary Endpoints

- Proportion of participants with  $\geq 1$  stage improvement in liver fibrosis (NASH CRN Fibrosis Score), with no worsening of NASH after 12 weeks of treatment (worsening of NASH is defined as an increase of the NAS by  $\geq 1$  point)
- Proportion of participants with  $\geq 2$  stage improvement in liver fibrosis (NASH CRN Fibrosis Score) after 12 weeks of treatment
- Proportion of participants with  $\geq 1$  stage improvement in liver fibrosis (modified Ishak score) after 12 weeks of treatment
- Proportion of participants with  $\geq 2$  stage improvement in liver fibrosis (modified Ishak score) after 12 weeks of treatment
- Change from baseline in CPA after 12 weeks of treatment
- Incidences of SAEs, AEs, clinical laboratory values, vital signs, physical examination findings, and ECGs
- Change from baseline in BMD, as measured by DXA scan, at Follow-up Week 24
- Plasma concentrations of siRNA, DPD, HEDC, and S104 (components of BMS-986263 for injection)

## 10.4 Statistical Analyses

The statistical analysis plan (SAP) will be finalized prior to the first unblinding event of the study and will provide detailed specifications of the analysis of all efficacy endpoints and safety and will also describe the populations used for analyses and procedures for accounting for missing, unused, and spurious data.

This section provides a summary of planned statistical analyses.

### 10.4.1 Efficacy Analyses

Efficacy analyses will be performed using the mITT population. Participants who discontinue early and do not have an ETT liver biopsy or otherwise have the result from the liver biopsy missing will be considered a “nonresponder” for the evaluation of the primary endpoint and other binary endpoints based on liver biopsy.

**Primary Endpoint:** To evaluate the effect of BMS-986263 (90 mg QW and 45 mg QW) on NASH CRN Fibrosis Stage at Week 12, a 95.0% confidence interval (CI) of response rate for treatment versus placebo will be used to estimate the difference between the proportions of participants with  $\geq 1$  stage improvement in fibrosis on liver biopsy. Additionally, the odds ratio will be used to estimate improvement of treatment as compared with placebo for the proportion of participants with  $\geq 1$  stage improvement in fibrosis on biopsy at Week 12. A logistic regression will be performed with platelet count as continuous independent covariate and stratified by the Randomization strata with a Z-test statistic at a two-sided significance level of  $\alpha=0.05$  to assess the difference in distribution of response rate separately between each BMS-986263 treatment group and placebo. To control for the family-wise (two-sided) Type I error rate of  $\alpha=0.05$ , the statistical tests will be performed in the following hierarchical order: 1) BMS-986263 90 mg versus placebo, and 2) BMS-986263 45 mg versus placebo. If the first comparison is not statistically significant, then the second comparison will be treated as descriptive in nature.

**Secondary [REDACTED] Endpoints:** No adjustment will be made for multiplicity for secondary [REDACTED] endpoints. Secondary [REDACTED] endpoints will be analyzed in a similar method as the primary endpoint unless otherwise specified in the SAP.

Selected continuous endpoints will be characterized using descriptive statistics and may be analyzed by analysis of covariance methods and/or by a mixed model for repeated measurements. Treatment differences at prespecified time points will be estimated using least squares means. Full details regarding this model and covariance structure will be provided in the SAP.

Categorical endpoints will be summarized using counts and percentages and when appropriate, may be analyzed using categorical analysis methods.

The stratified log-rank test and Kaplan-Meier estimate may be used to analyze time-to-event endpoints and will be specified in the SAP.

Subgroup analyses may be performed as specified in the SAP.

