#### Study Treatment:

Study Drug for IM025017		
Medication	Potency	IP/Non-IP
BMS-986263 for injection	10 mg per vial; 3 mg/mL after reconstitution	IP
Placebo a for BMS-986263 for injection/on-site compounded sterile dosage form	NA	IP

IP = investigational product; IV = intravenous; NA = not applicable

a [REDACTED]

**Statistical Methods:** Efficacy analyses will be performed using the modified intent-to-treat population. Participants who discontinue early and do not have an Early Treatment Termination liver biopsy or otherwise have the result from the liver biopsy missing will be considered a “nonresponder” for the evaluation of the primary endpoint and other binary endpoints based on liver biopsy.

**Primary Endpoint Analysis:** To evaluate the effect of BMS-986263 (90 mg QW and 45 mg QW) on NASH CRN Fibrosis Stage at Week 12, a 95.0% confidence interval of response rate for active treatment versus placebo will be used to estimate the difference between the proportions of participants with  $\geq 1$  stage improvement in fibrosis on liver biopsy. Additionally, the odds ratio will be used to estimate improvement of treatment as compared with placebo for the proportion of participants with  $\geq 1$  stage improvement in fibrosis on biopsy at Week 12. A logistic regression will be performed with platelet count as independent covariate and stratified by the Randomization strata with a Z-test statistic at a two-sided significance level of  $\alpha=0.05$  to assess the difference of response rate separately between each BMS-986263 treatment group and placebo. To control for the family-wise (two-sided) Type I error rate of  $\alpha=0.05$ , the statistical tests will be performed in the following hierarchical order: 1) BMS-986263 90 mg versus placebo, and 2) BMS-986263 45 mg versus placebo. If the first comparison is not statistically significant, then the second comparison will be treated as descriptive in nature.

**Secondary [REDACTED] Endpoint Analyses:** No adjustment will be made for multiplicity for secondary [REDACTED] endpoints. Secondary [REDACTED] endpoints will be analyzed in a similar method as the primary endpoint unless otherwise specified in the statistical analysis plan (SAP).

[figure not shown]

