### **5.1.2 *Treatment Period and Follow-up***

Participants meeting eligibility criteria during the screening period will enter the treatment period. Approximately 270 participants will be randomized via interactive response technology (IRT) in a 1:1:1 ratio to receive 45 mg BMS-986263 QW, 90 mg BMS-986263 QW, or placebo QW by IV infusion in a double-blind manner.

Participants will be stratified at Randomization by the presence of definite steatohepatitis on biopsy (yes versus no). At least 80% of participants will be required to have definite steatohepatitis on the biopsy used to confirm eligibility. Participants will receive study treatment via IV infusion for a total of 12 weeks. Liver biopsy will be performed at Week 12.

After 12 weeks (Day 85) of treatment or after early treatment discontinuation, participants will enter the 24-week follow-up period, during which participants will not receive investigational treatment. After all participants complete the Follow-up Week 4 visit, the study will be unblinded and analyses of the available Week 12 data will be conducted ([Section 10.4.4](#)). Participants who discontinue study treatment before the Week 11 Visit will have an Early Treatment Termination (ETT) visit and will continue into the 24-week follow-up period.

See the SOA in [Table 2](#) and [Table 3](#) ([Section 2](#)).

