g) Liver biopsy performed within 12 months prior to the screening visit or performed during the screening period. A liver biopsy performed prior to ICF, if utilized for eligibility, must be available for central pathology reading prior to Randomization.

i) Liver biopsy consistent with NASH CRN Fibrosis Score Stage 4, as assessed by central pathology reading.

ii) Liver biopsy must either be consistent with steatohepatitis, as assessed by central pathology reading, OR, for liver biopsies without definite steatohepatitis, there should be some evidence of steatosis and/or ballooning and the following definition of NASH cirrhosis must be fulfilled:

(1) Absence of other causes of liver disease AND either of the following:

(a) At least 2 of the 3 following criteria:

(i) History of body mass index (BMI)  $\geq 30 \text{ kg/m}^2$

(ii) History of type 2 diabetes mellitus

(iii) History of hypertension AND/OR history of dyslipidemia

OR

(b) Previous histologic readings of steatohepatitis (in a past biopsy prior to the one utilized for eligibility) AND either history of BMI  $\geq 30 \text{ kg/m}^2$  OR history of type 2 diabetes mellitus.

NOTE: At least 80% of participants will be required to have definite steatohepatitis on the biopsy used to confirm eligibility.

h) Participants taking sodium glucose cotransporter 2 (SGLT2) inhibitors, glucagon-like peptide-1 (GLP-1) receptor agonists, anti-obesity agents, or approved NASH treatment must have been on stable doses for at least 3 months prior to screening.

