**Modified Ishak Score**

A modified Ishak scoring system^40 will be used as a secondary endpoint to grade fibrosis in the histologic samples. The Ishak system (0 to 6 scale) was originally developed to grade portal-based liver fibrosis associated with viral hepatitis. The modified Ishak system has been adapted to grade central-based liver fibrosis associated with NASH, and it also uses a 0 to 6 scale:

- 0: No fibrosis
- 1: perisinusoidal or periportal fibrosis
- 2: perisinusoidal and portal/periportal fibrosis
- 3: bridging fibrosis with linkage of < 50% of vascular structures (portal and centrilobular)
- 4: bridging fibrosis with linkage of > 50% of vascular structures (portal and centrilobular)
- 5: early or incomplete cirrhosis

- 6: established or advanced cirrhosis

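### Optional efficiency gain, not an error: adding baseline modified Ishak stage (5 vs 6) to the primary logistic model would raise power by 0 to about 3 points (90 mg) and 0 to about 7 points (45 mg), under assumed prognostic effects

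*Combined protocol and SAP*

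**What the plan says.** Section 10.4.1 defines the primary test as a Wald-type Z-test from a logistic model: "A logistic regression will be performed with platelet count as continuous independent covariate and stratified by the Randomization strata". The synopsis (Section 1.1, Statistical Methods) repeats it: "A logistic regression will be performed with platelet count as independent covariate and stratified by the Randomization strata". Section 5.1.2 names the single stratification factor: "Participants will be stratified at Randomization by the presence of definite steatohepatitis on biopsy (yes versus no").

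Inclusion criterion 2 g) in Section 6.1 fixes the baseline CRN stage for everyone: "Liver biopsy consistent with NASH CRN Fibrosis Score Stage 4, as assessed by central pathology reading". The modified Ishak scale in Section 9.1.2.1 divides cirrhosis in two, "5: early or incomplete cirrhosis" and "6: established or advanced cirrhosis". Section 10.3.2 lists two responder endpoints on that scale, at thresholds of 1 and 2 stages, each worded as "stage improvement in liver fibrosis (modified Ishak score) after 12 weeks of treatment". Section 9.1.2 lists the modified Ishak score among the histological efficacy assessments.

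On timing, Section 10.4 says: "The statistical analysis plan (SAP) will be finalized prior to the first unblinding event of the study". Section 10.4.5 allows interim analyses at about 30% and 50% of participants.

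**The concern.** The primary endpoint is a drop of at least one CRN stage, and all participants start at Stage 4. Baseline CRN stage is therefore a constant and cannot explain any variation in response. Platelet count and steatohepatitis status are the only baseline variables in the stated model.

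The protocol's own scales suggest that baseline Ishak stage could be prognostic. CRN Stage 3 is bridging fibrosis, and on the modified Ishak scale bridging is stage 3 or 4. A participant at Ishak 5 is thus one stage from leaving cirrhosis, and a participant at Ishak 6 is two. That supports a direction but says nothing about size.

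Adjusting for a covariate that truly predicts response raises the power of the treatment test and accounts for chance imbalance in that covariate. The 90 mg comparison, tested first, already has ample power. The likely beneficiary is the 45 mg comparison, which has little margin over 80% and is tested formally only if 90 mg succeeds.

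**Working it through.** **Inputs from the protocol.** Response rates are 45% (90 mg), 40% (45 mg) and 20% (placebo). There are 85 evaluable and about 90 randomized per arm, with 6% dropout (Section 10.1). The test is two-sided at 0.05, a missing biopsy counts as nonresponse, and 90 mg is tested before 45 mg (Section 10.4.1).

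**Inputs assumed, because the documents give none.** These are the odds ratio (OR) for response at Ishak 5 versus 6, varied from 1 to 8, and the share of participants at Ishak 5, 50% in the main case.

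**Step 1: reproduce the stated power.** For a two-group chi-square test without continuity correction, where p̄ is the mean of the two rates,

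power = Φ{ [ |p₁ − p₀|·√n − 1.96·√(2p̄(1 − p̄)) ] / √(p₁(1 − p₁) + p₀(1 − p₀)) }.

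- 45 mg, n = 85: (0.20 × 9.220 − 1.96 × 0.648) / 0.632 = 0.907, so power is 81.8%.
- 90 mg, n = 85: (0.25 × 9.220 − 1.96 × 0.662) / 0.638 = 1.577, so power is 94.3%.

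The claim of at least 80% holds for both doses.

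With all 90 per arm analysed and 6% set to nonresponse, the rates become 0.45 × 0.94 = 42.3%, 0.40 × 0.94 = 37.6% and 0.20 × 0.94 = 18.8%. The same formula then gives 93.5% (90 mg) and 80.6% (45 mg).

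**Step 2: simulate the model with and without Ishak stage.** Response is generated as logit P = a + b·treatment + ln(OR)·[Ishak 5]. The constants a and b are solved so that the overall rates before missing data stay at 45% or 40% versus 20%. As a check at OR 8, placebo response is 34.0% at Ishak 5 and 6.0% at Ishak 6. The mean is (34.0 + 6.0)/2 = 20.0%, and (0.34/0.66)/(0.06/0.94) ≈ 8.

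Model 1 has treatment, platelet count and the steatohepatitis stratum (80% yes). Model 2 adds the Ishak 5 indicator. Each scenario uses 90 per arm, 6% set to nonresponse at random and 30,000 trials. The Monte Carlo standard error of the paired gain is at most 0.17 points.

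| OR, Ishak 5 vs 6 | Placebo response at 5 / 6 | 90 mg power, without → with (gain) | 45 mg power, without → with (gain) |
|---|---|---|---|
| 1 | 20.0% / 20.0% | 93.4% → 93.4% (0.0) | 80.4% → 80.4% (0.0) |
| 2 | 25.4% / 14.6% | 93.3% → 93.6% (0.3) | 80.4% → 81.0% (0.6) |
| 4 | 30.2% / 9.8% | 93.4% → 95.0% (1.6) | 80.5% → 83.7% (3.2) |
| 8 | 34.0% / 6.0% | 93.4% → 96.4% (3.0) | 80.6% → 86.4% (5.8) |

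**Step 3: sensitivity at OR 8** (10,000 trials each; standard error of the gain at most 0.31 points).

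- 25% at Ishak 5: gain 3.2 points (90 mg) and 6.6 (45 mg).
- 75% at Ishak 5: gain 1.5 and 2.8.
- Platelet count itself prognostic (OR 1.5 per SD) and correlated 0.5 with the Ishak split: gain 1.9 and 4.3.

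**Step 4: independent check.** A separately written simulation fitted all three arms in one model, with 10,000 trials per scenario. At 85 per arm and a 50% split, OR 8 gave 93.9% → 97.3% (90 mg) and 81.7% → 88.0% (45 mg). Across its scenarios the gain ran from 0 to 3.5 points (90 mg) and from 0 to 7.7 (45 mg); the 7.7 is at OR 8 with 30% at Ishak 5. Power to succeed on both doses in the hierarchy rose by 0 to about 9 points. With no prognostic effect, any loss was at most 0.2 points, within simulation error.

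**Step 5: type I error.** Under the null, two-sided rejection without and with the term was 4.8% and 4.9% at OR 1, and 5.2% and 5.2% at OR 8 (20,000 trials each). There is no material inflation.

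**The case against.** The case against is that this is a preference. The planned model is valid and meets its power target, and almost any trial could add a covariate. Baseline collagen proportionate area, also needed for a secondary endpoint, would be another candidate. Nothing in the documents shows that Ishak 5 versus 6 predicts CRN response. The top of the range needs an OR of 8, a very strong effect among people who all have cirrhosis. At an OR of 2 to 3 the gain is roughly 0.3 to 1.2 points for 90 mg and 0.5 to 2.4 for 45 mg. A lopsided split also shrinks it: with 90% at Ishak 5, even an OR of 8 gives only 0.9 and 1.1 points. The larger gain goes to the comparison that becomes descriptive if 90 mg fails.

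All of that stands as a limit on size. It does not show harm, because the cost when the covariate is uninformative is close to zero.

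Three further points also stand:

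- The protocol section is a summary, and the SAP, which was not available, may already add covariates.
- The odds ratio becomes conditional on one more variable, and missing baseline Ishak scores need a rule.
- Section 10.4.1 also reports a confidence interval for the difference in proportions and does not say it is covariate-adjusted. The simulated gain applies to the Wald test, not to an unadjusted interval.

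Appendix 9 records that Revised Protocol 02 moved platelet count from stratification into the model, so adjustment was actively considered. The reason given concerns the number of stratification factors and does not argue against a model covariate.

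**Conclusion.** The point holds as an optional improvement; there is no error in the plan. The stated primary model leaves out a baseline fibrosis measure that the trial must collect anyway and that can separate participants who are identical on the CRN scale. The gain is 0 to about 3 points of power for 90 mg and 0 to about 7 for 45 mg; the independent check reached 3.5 and 7.7.

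The range rests on an assumed OR of 1 to 8 and an assumed Ishak split, which the documents cannot narrow. Modest effects give gains near the bottom of it. The absence is shown for the protocol text only. This is worth considering, with medium confidence in the size of the benefit.

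**What to change.** Add baseline modified Ishak stage from the centrally read eligibility biopsy, coded 6 versus 5 or lower, as one binary covariate in the primary logistic model and the other fibrosis-response models. State how a missing baseline score is handled, and whether the confidence interval for the difference in proportions uses the same adjustment. Do this before the first unblinding event, which may be the 30% interim analysis, since a covariate chosen after unblinding loses credibility.

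The main change is one sentence each in Section 10.4.1, the synopsis and the SAP. It needs no new data and uses one degree of freedom. The reported odds ratio becomes conditional on Ishak stage as well, and the text should say so.

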#### **10.4.2 Safety Analyses**

Safety analyses will be performed using the safety population. For analysis, all treatment-emergent AEs recorded that occur during the conduct of the study will be listed and summarized by system organ class, preferred term, and treatment. Vital signs and clinical laboratory test results will be listed and summarized by treatment. ECG readings will be evaluated by the investigator and abnormalities, if present, will be summarized and listed.

Safety assessments include incidences of AEs, SAEs, and AESI (Section 9.2), AEs leading to discontinuation, and death, as well as marked abnormalities in clinical laboratory tests, vital sign measurements, ECGs, physical examinations, and change in BMD collected by DXA scan from baseline to Follow-up Week 24. Furthermore, the occurrence of IRRs will be analyzed as a function of the infusion rates and compared between treatment groups.

[REDACTED]

##### **10.4.3.1 PK [REDACTED]**

PK [REDACTED] of BMS-986263 will be analyzed based on the time points indicated in [REDACTED]. Plasma concentrations of the components of the LNP, such as DPD, S104, and HEDC will also be measured.

PK evaluation is a secondary endpoint. Plasma concentrations of siRNA, DPD, HEDC, and S104 (components of BMS-986263 for injection) will be listed and summarized descriptively by dose, day, and time.

[REDACTED]

Analysis of PK and exposure-response relationships of BMS-986263 will be conducted using a population approach as appropriate and reported separately from the CSR.

[REDACTED]

#### **10.4.4 Week 12 Analyses**

After all participants have either completed the Follow-up Week 4 visit or have discontinued the study prior to the Follow-up Week 4 visit, the study will be unblinded and the primary analysis for the study will be conducted.

#### **10.4.5 Interim Analysis**

Two interim analyses may be performed after approximately 30% and 50% of participants have either completed the Follow-up Week 4 visit or have discontinued the study prior to the Follow-up Week 4 visit.

The purpose of the 30% interim analyses will be to assess futility. The DMC will review the available data to make recommendation on the following options:

- Continue the study as planned
- Terminate the study for futility

The futility decision criteria and the review process by the DMC will be specified in the DMC Charter and the DMC SAP.

The purpose of the 50% interim analysis will be to help in early planning for accelerating further clinical development of the compound. No formal test of statistical significance is planned. Results will be descriptive and based on the estimation of effect size and associated CIs. Thus, no adjustments to overall Type I error will be made.

The interim analysis results on both occasions will be reviewed by the independent DMC; and the Sponsor's Internal Review Committee (IRC) if needed. The blinding to investigators and the study team will be maintained until the end of the study.

Within the DMC Charter, for each interim analysis, the Sponsor will specify:

- Conditions under which interim results could be shared with select individuals within BMS to help in early planning of clinical development of the compound
- Steps taken to ensure the blinding of the other BMS personnel (that are not unblinded) and investigators to interim results
- Statistical summaries that will be prepared for review

Details of the interim analyses will be described in the DMC SAP and DMC Charter, which will be revised and finalized prior to the DMC meeting.

**12 APPENDICES**

**APPENDIX 1 ABBREVIATIONS AND TRADEMARKS**

Term	Definition
AE	adverse event
AESI	adverse events of special interest
AFP	alpha-fetoprotein
ALP	alkaline phosphatase
ALT	alanine aminotransferase
APRI	AST-to-platelet ratio index
AST	aspartate aminotransferase
AUC	area under the plasma drug concentration-time curve
AUC(INF)	area under the concentration-time curves from zero to infinity
AUC(0-T)	area under the concentration-time curves from time zero to the time of the last quantifiable concentration
BIW	twice per week
BMD	bone mineral density
BMI	body mass index
BMS	Bristol-Myers Squibb
BUN	blood urea nitrogen
C3M	matrix metalloproteinase-derived collagen Type III-specific neoepitope peptide
CBC	complete blood count
CFR	Code of Federal Regulations
CI	confidence interval
CL	total plasma clearance
Cmax	maximum observed plasma concentration
CMH	Cochran-Mantel-Haenszel
COVID-19	coronavirus disease 2019
CPA	collagen proportionate area
CRN	Clinical Research Network
CSR	clinical study report
CT	computed tomography
DILI	drug-induced liver injury
DMC	Data Monitoring Committee
DMN	dimethylnitrosamine
DNA	deoxyribonucleic acid
DPD	di-retinamide-PEG-di-retinamide

DXA	dual-energy X-ray absorptiometry
ECG	electrocardiogram
eCRF	electronic case report form
ELF	enhanced liver fibrosis
ePRO	electronic patient-reported outcomes
EOS	End of Study
EST	Early Study Termination
ETT	Early Treatment Termination
FDA	Food and Drug Administration
FIB-4	Fibrosis-4
FSH	follicle-stimulating hormone
GFR	glomerular filtration rate
GGT	gamma-glutamyl transferase
GLP-1	glucagon-like peptide-1
HbA1c	hemoglobin A1c
HbcAb	hepatitis B core antibody
HbsAb	hepatitis B surface antibody
HbsAg	hepatitis B surface antigen
HBV	hepatitis B virus
HCC	hepatocellular carcinoma
HCV	hepatitis C virus
HDL	high-density lipoprotein
HEDC	(Bis[2-(tetradecanoyloxy)ethyl] carbamoylmethyl)-(2-hydroxyethyl)dimethylazanium bromide
HI	hepatic impairment
HIV	human immunodeficiency virus
HSC	hepatic stellate cell
HSP47	heat shock protein 47
IB	Investigator's Brochure
ICF	informed consent form
IEC	Independent Ethics Committee
IMP	investigational medicinal product
INR	international normalized ratio
IP	investigational product
IPRC	Independent Pathology Review Committee
IRB	Institutional Review Board
IRR	infusion-related reaction
IRT	interactive response technology
IV	intravenous
LAM	lactational amenorrhea method
LDH	lactate dehydrogenase
LDL	low-density lipoprotein

LNP	lipid nanoparticle
MCH	mean corpuscular hemoglobin;
MCV	mean corpuscular volume
MELD	Model for End-stage Liver Disease
miITT	modified intent-to-treat
MRE	magnetic resonance elastography
MRI	magnetic resonance imaging
mRNA	messenger ribonucleic acid
NAFLD	nonalcoholic fatty liver disease
NAS	NAFLD Activity Score
NASH	nonalcoholic steatohepatitis
NOAEL	no-observed-adverse-effect level
OTC	over-the-counter
PK	pharmacokinetics
PRO-C3	N-terminal Type III collagen propeptide
PT	prothrombin time
PTH	parathyroid hormone
PTT	partial thromboplastin time
QW	once every week
RBC	red blood cell
RNA	ribonucleic acid
RNAi	ribonucleic acid interference
RT-PCR	reverse transcription - polymerase chain reaction
SAE	serious adverse event
SAP	statistical analysis plan
SARS-CoV-2	severe acute respiratory syndrome coronavirus 2
SGLT2	sodium glucose cotransporter 2
siRNA	small interfering ribonucleic acid
SOA	Schedule of Activities
SVR	sustained virologic response
TEAE	treatment emergent adverse event
ULN	upper limit of normal

WBC	white blood cell
WOCBP	women of childbearing potential

